#### 4.2.8 Analyses of Safety

All safety variables will be summarized for patients in the SP using descriptive statistical methods stratified by treatment regimen and cirrhosis status and overall.

An overview of tables for the individual values is given in Table 13.

The layouts of the tables mentioned above are provided in Part II of the SAP (Table Shells).

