**Confidential Information**

No use or disclose outside AbbVie is permitted without prior written authorization from AbbVie

relapse rates will be estimated in patients of the CP analysis groups with EoT response and sufficient HCV RNA measurements post treatment. Viral breakthrough rates will be estimated in all patients of the CP analysis groups, who have at least one undetectable HCV RNA measurement on treatment and at least one on-treatment or EoT measurement thereafter. For all rates specified above 95%- confidence intervals (CIs) will be determined using the Wilson Score method.

Univariate and multiple logistic regression (MLR) methods will be used to investigate the impact of various explanatory covariates (e.g. demographic and disease characteristics, co-morbidities, type of treating institution, and prior treatment for CHC and response outcome in treatment experienced patients) on SVR12. These analyses will be of exploratory nature, data driven, and will be performed in the CP. Backward selection procedures will be applied to generate the final MLR models. A p-value <0.05 will be used for the covariates to stay in the model in a backward elimination step. Logistic regression methods will also be used to investigate the impact of treatment adherence on SVR12.

All safety variables will be summarized for patients in the SP using descriptive statistical methods stratified by the type of combination treatment.

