#### Confidential Information

### **9.2.2 Study Duration**

This is a prospective, observational study. The inclusion period will be approximately 12 months and the observational period of the study will be from baseline visit until 48 weeks post-treatment.

The observational period for patients receiving 12 weeks of ABBVIE REGIMEN will be max. 60 weeks (12 weeks treatment and 48 weeks post-treatment observation) and for patients receiving 24 weeks of ABBVIE REGIMEN the observational period will be max. 72 weeks (24 weeks treatment and 48 weeks post-treatment observation).

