## **9.7.6 Tolerability Analysis**

All tolerability variables will be summarized using descriptive statistical methods for the SP stratified by type of combination treatment and scheduled treatment duration.

All SAEs, non-serious AEs and pregnancy occurrences are to be reported for patients included in the study (see Section 11.0 and 9.2.3). AEs will be coded using MedDRA. The number and percentage of patients with treatment-emergent AEs (i.e. any reported event that begins or worsens in severity after initiation of study drug through 30 days post-study drug dosing) will be tabulated by primary MedDRA SOC and PT. Corresponding summary tables will be provided for all serious treatment-emergent AEs. The tabulation of the number of patients with treatment-emergent AEs by severity and relationship to study drug will also be provided. Patients reporting more than one AE for a given MedDRA PT will be counted only once for that term using the most severe incident for the severity summary table and the most related for the relationship summary table. Patients reporting more than one type of event within a SOC will be counted only once for that SOC.

Additional details of the analysis of AEs will be specified in the SAP.

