### SP analysis groups

The SP analysis groups are defined according to the treatment regimen and patient's fibrosis status. The standard summaries by SP groups in the safety population are as follows (if not specified otherwise):

- Total (regardless of cirrhosis status)
  - (1) Total
  - (2) 2DAA w/o RBV
  - (3) 2DAA + RBV
  - (4) 3DAA w/o RBV
  - (5) 3DAA + RBV
- Patients with cirrhosis
  - (6) Total
  - (7) 2DAA w/o RBV
  - (8) 2DAA + RBV
  - (9) 3DAA w/o RBV
  - (10) 3DAA + RBV
- Patients without cirrhosis
  - (11) Total
  - (12) 2DAA w/o RBV
  - (13) 2DAA + RBV
  - (14) 3DAA w/o RBV
  - (15) 3DAA + RBV
- Patients with unknown fibrosis status
  - (16) Total
  - (17) 2DAA w/o RBV
  - (18) 2DAA + RBV
  - (19) 3DAA w/o RBV
  - (20) 3DAA + RBV

(2DAA - paritaprevir/r-ombitasvir, 3 DAA - paritaprevir/r-ombitasvir + dasabuvir, RBV – ribavirin taken, w/o RBV – no ribavirin taken)

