#### **4.2.8.3 Adverse Events**

All tolerability variables will be summarized using descriptive statistical methods for the SP stratified by treatment regimen and cirrhosis status and overall.

AEs will be coded using MedDRA. A glossary will show the verbatim terms and the corresponding coded terms used (see Table 13).

The number and percentage of patients with treatment-emergent AEs (i.e. any reported event that begins or worsens in severity after initiation of study drug through 30 days post-study drug dosing including those who are related to the study drug independent of the occurrence and those where the date of onset is missing) will be tabulated by primary MedDRA SOC and PT.

Corresponding summary tables will be provided for all serious treatment-emergent AEs and additional for all non-serious treatment-emergent AEs. In the table of non-serious AEs (that must exclude any SAE) only preferred terms that occurred at a frequency of  $\geq 5\%$  in any treatment group will be displayed (no SOCs will be displayed).

The tabulation of the number of patients with treatment-emergent AEs by severity (AEs by severity [mild, moderate, severe], AEs leading to death, AEs leading to hospitalization) and relationship to study drug will also be provided (ABBVIE regimen, ribavirin, medication error -

paritaprevir/r-ombitasvir, medication error – dasabuvir, ABBVIE regimen withdrawn, ribavirin withdrawn).

Patients reporting more than one AE for a given MedDRA PT will be counted only once for that term using the most severe incident for the severity summary table and the most related for the relationship summary table. Patients reporting more than one type of event within a SOC will be counted only once for that SOC.

The frequency of pregnancies will be displayed as well.

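### The SAP replaces scheduled treatment duration with cirrhosis status in the safety tables without declaring it, so cells mixing 12- and 24-week courses can show higher crude AE percentages through longer observation alone

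*SAP*

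**What the plan says.** - **Protocol 9.7.6 (Tolerability Analysis)** summarises tolerability in the safety population (SP) "stratified by type of combination treatment and scheduled treatment duration". It leaves further detail of the AE analysis to the SAP.
- **Protocol abstract (Data Analysis)** is less specific: safety is summarised "stratified by the type of combination treatment", with no mention of duration.
- **SAP 4.2.8** summarises all safety variables "stratified by treatment regimen and cirrhosis status and overall", and SAP 4.2.8.3 repeats this for adverse events: "for the SP stratified by treatment regimen and cirrhosis status and overall".
- **SAP 4.2.1 (SP analysis groups)**: "The SP analysis groups are defined according to the treatment regimen" and fibrosis status. Regimen here means two or three direct-acting antivirals, with or without ribavirin. There are 20 groups and none is defined by duration. The stratified AE outputs in SAP Table 12 carry the same regimen-by-cirrhosis title.
- **SAP 4.2.8.3** reports treatment-emergent AEs as numbers and percentages of patients, counted from first dose to 30 days after dosing. Drug-related events at any time and events with missing onset date are added. No exposure-adjusted rate is planned.
- **SAP 4.2.8.1** summarises duration of treatment descriptively, in an output with the same column structure.

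**The concern.** A crude percentage of patients with an event depends on how long each patient is observed. Protocol 9.7.6 keeps 12- and 24-week courses apart, so each percentage refers to one length of observation. The SAP's cells do not. If 24-week patients are unevenly spread over the regimen-by-cirrhosis cells, the cells holding more of them will tend to show higher percentages even when tolerability per unit of time is identical. A reader of adjacent columns could then credit ribavirin or cirrhosis with an excess that comes from the observation window.

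The change is also silent. The SAP does declare other departures from the protocol, namely the upper bound on the SVR12 window (4.1.1) and the replacement of laboratory shift tables (4.2.8.4). This one is neither declared nor justified.

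**Working it through.** **1. Stratifiers side by side**

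| Source | Combination / regimen | Scheduled duration | Cirrhosis |
|---|---|---|---|
| Protocol abstract | yes | no | no |
| Protocol 9.7.6 | yes | yes | no |
| SAP 4.2.8, 4.2.8.3, SP groups, Table 12 | yes | no | yes |

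**2. Time at risk**

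The plan states no time at risk for AEs. Its related figures are the maximum observation periods in Protocol 9.2.2: "12 weeks treatment and 48 weeks post-treatment observation" (12 + 48 = 60 weeks) and "24 weeks treatment and 48 weeks post-treatment observation" (24 + 48 = 72 weeks). Both totals agree with the text. The treatment-emergent window is treatment days plus 30:

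- 12-week course: 12 × 7 + 30 = 84 + 30 = 114 days
- 24-week course: 24 × 7 + 30 = 168 + 30 = 198 days
- Ratio: 198 / 114 = 1.74. For on-treatment time alone it is 168 / 84 = 2.0.

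These are planned windows for completed courses. The added drug-related and missing-onset events are not bounded by them.

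**3. Where durations can mix**

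- Protocol 7.1 describes a trial in cirrhotic genotype 1 patients, all given ribavirin and randomised to 12 or 24 weeks. It reads the results as pointing to the longer course only for cirrhotic genotype 1a prior null responders. This is background evidence, not a rule of this study.
- SAP 4.2.7.2.1 gives 12 versus 24 weeks as an example of a comparison within cirrhotic genotype 1 patients, so both durations are expected there.
- Mixing is therefore most plausible in the cirrhotic ribavirin-containing cells and in the total columns. It may be small in the non-cirrhotic cells.
- The second interim analysis restricts the SP to planned 12-week treatment, and the third also describes such a restriction. None is stated for the fourth, the fifth or the final safety analysis.

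**4. Size in a pooled cell (illustration)**

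The documents give neither the share *s* of 24-week patients nor AE risks, so both are assumed. With the same constant hazard in both courses:

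- p24 = 1 − (1 − p12)^(198/114)
- pooled percentage = (1 − s) × p12 + s × p24

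For p12 = 30%: p24 = 1 − 0.70^1.737 = 46.2%. With s = 25%: 0.75 × 30 + 0.25 × 46.2 = 34.0%.

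| p12 | p24 | pooled, s = 10% | s = 25% | s = 50% |
|---|---|---|---|---|
| 5% | 8.5% | 5.4% | 5.9% | 6.8% |
| 10% | 16.7% | 10.7% | 11.7% | 13.4% |
| 30% | 46.2% | 31.6% | 34.0% | 38.1% |
| 50% | 70.0% | 52.0% | 55.0% | 60.0% |
| 70% | 87.6% | 71.8% | 74.4% | 78.8% |

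Under the same assumption the rate does not depend on duration: −ln(0.70) / 114 × 36,525 = 114.3 per 100 patient-years for either course.

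**5. Early events**

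Protocol 7.1 reports bilirubin elevations peaking by Week 1 and transient ALT elevations. If every event of a type fell early in the period common to both courses, the pooled figure would stay at p12. For a 30% risk and shares up to 50%, the illustration thus runs from no inflation to 38.1%.

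**The case against.** The case against giving this much weight is substantial.

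- **The objective is descriptive.** Both documents aim to describe tolerability, and no test or contrast of AEs between regimens is planned. The percentage with an event over the prescribed course is a legitimate description. This stands. A reader might infer that the objective is answered by comparing regimen columns and that the comparison is invalid, but neither document plans that comparison.
- **The protocol is not uniform.** The abstract names combination type only, and 9.7.6 leaves AE detail to the SAP. A reader might infer that the protocol had firmly controlled for exposure time. That is too strong. Still, 9.7.6 is the detailed section, and it names duration.
- **Cirrhosis is a partial proxy for duration.** This also stands. It limits the problem mainly to the cells named above, but does not remove it where the SAP itself expects both durations.
- **Exposure is tabulated in matching columns.** A reader can see that a cell has longer treatment, which lowers the risk of misreading. The table gives no means of adjusting the AE percentage.
- **A full duration split is unwieldy.** Crossing 20 groups with two durations gives up to 40 columns, many probably sparse. This argues for a limited split or for rates, not for leaving the tables unchanged.

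**Conclusion.** The departure from Protocol 9.7.6 is real and undeclared. Crude percentages in cells that mix durations can be raised by longer observation alone. The firm figure is the ratio of planned windows, 198 / 114 = 1.74. The effect on any table cannot be fixed from the documents. At a 12-week risk of 30% it would be about 1.6, 4.0 or 8.1 percentage points for 24-week shares of 10%, 25% or 50%, assuming constant hazard and completed courses, and smaller for early-onset events.

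It is tempting to take the rise from 30% to 46.2% as the size of the problem. That step compares a purely 12-week group with a purely 24-week group, whereas the SAP's cells are pooled. Nor do the documents show that the safety tables are distorted throughout. This is an inexpensive improvement to the reporting, together with a discrepancy to be declared.

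**What to change.** 1. Keep regimen by cirrhosis status as the main structure.
2. In the treatment-emergent AE and SAE tables, do one of the following:
   - add exposure-adjusted rates per 100 patient-years beside the crude percentages, using each patient's actual time at risk; or
   - split by scheduled duration (12 versus 24 weeks) within the cirrhotic strata and the total columns only.
3. If rates are used, state how patients are counted and when their time at risk ends, and how drug-related events outside the window and events with missing onset enter the numerator.
4. Declare and justify the departure from Protocol 9.7.6 in SAP 4.2.8, and reconcile it with the protocol abstract.

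No new data are needed: planned duration already served to restrict interim populations, and actual duration is summarised in SAP 4.2.8.1. The cost is extra columns. The duration split will leave some small cells. Rates avoid those but lean on a roughly constant hazard and can flatter the longer course when events come early, so they should stand beside the crude percentages and not replace them.

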##### 4.2.8.1 Exposure to Study Medication

One table will show the frequencies for early discontinuation and exceedance of ABBVIE regimen or ribavirin and the corresponding reasons for SP by treatment regimen and cirrhosis status. The ABBVIE regimen is considered to have been prematurely discontinued if actual duration is shortened for more than 7 days. The duration for taking ABBVIE regimen is considered to have been exceeded if the actual duration is prolonged for more than 7 days. Furthermore, summary statistics will be generated for the duration of ABBVIE regimen taken and the duration of ribavirin taken, i.e. n, mean, median, standard deviation [SD], minimum, maximum.

Unintended medication errors, i.e. patient missed taking Paritaprevir/r-Ombitasvir or Dasabuvir for at least 7 days in a row, will be displayed by medication for the entire treatment period.

#### 4.2.8.2 Co-medication

Treatments, surgical and medical procedures will be coded by ABBVIE assigning appropriate preferred and class terms. Frequencies will be displayed for SP by treatment regimen and cirrhosis status.

In one table, the co-medication (preferred term) will be grouped by class. Only co-medication received during treatment specified by ABBVIE regimen will be displayed (Treatment profiles: A1, A2, C1 Drug B, C2 Drug B, C3 Drug B, D).

In another table, the co-medication (preferred term) will be grouped by profile. All treatment profiles will be considered, i.e.:

- A1: Continued (A1)
- A2: Permanently discontinued during CHC treatment (A2)
- A3: Permanently discontinued prior to CHC treatment (A3)
- B: Discontinued prior to CHC treatment and reintroduced post-treatment (B)
- C1 Drug A: Permanently replaced at start of CHC treatment (C1A)
- C1 Drug B: Substitute at start of CHC treatment and discontinued during CHC treatment (C1B)
- C2 Drug A: Permanently replaced at start of CHC treatment (C2A)
- C2 Drug B: Substitute at start of CHC treatment and continued (C2B)
- C3 Drug A: Replaced during CHC treatment (C3A)
- C3 Drug B: Substitute during CHC treatment (C3B)
- D: Introduced during CHC treatment (D)
- No profile reported: No profile reported

Another table will show the associated treatment profiles for the medications of special interest. Therefore the medication will be pooled appropriately. All treatment profiles will be considered.

A further table will show the associated treated conditions, i.e.:

- Alcoholic liver disease
- Angina pectoris
- Auto-immune hepatitis
- Auto-immune skin disease
- Bipolar disorder
- Chronic kidney disease
- Cryoglobulinemia
- Depression
- Diabetes mellitus (Type 1)
- Diabetes mellitus (Type 2)
- Hemophilia
- Hepatitis B
- Hepatocellular carcinoma
- HIV
- Hypertension
- Hyperthyroidism
- Hypothyroidism
- Immunologically mediated disease
- Insulin resistance

- Kidney transplantation
- Lipid disorder
- Liver transplantation
- Metabolic syndrome
- Myocardial infarction
- Opiate substitution
- Personality disorder
- Porphyria cutanea tarda (PCT)
- Primary biliary cirrhosis
- Schistosomiasis
- Schizophrenia
- Sickle cell anemia
- Steatosis (non-alcoholic)
- Stroke
- Thalassemia
- Tuberculosis
- v. Willebrand disease
- Wilson disease
- Other

All treatment profiles will be considered.

One table will displays the number of patients taking herbals except St. John's Wort, homeopathics or other drugs for which neither a name nor a profile nor a treated condition had to be reported. These medications will be excluded from the other co-medication tables.

A glossary will show the verbatim terms and the corresponding coded terms used (see Table 13).

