The ABBVIE REGIMEN has been studied with and without RBV in over 2,300 patients in Phase III trials across a variety of patient populations including those with compensated cirrhosis. Based on Phase III data, the ABBVIE REGIMEN, with or without RBV, was well tolerated with a low discontinuation rate. Adverse events (AEs) were typically mild, and many of the AEs and laboratory abnormalities reported were attributable to the presence of RBV. However, these AEs were much milder than observed when RBV was given in combination with interferon. Transient, asymptomatic serum alanine aminotransferase (ALT) elevations were observed at a low rate, were not associated with hepatic dysfunction and generally resolved with ongoing treatment. A disproportionate number of the cases were in women on concurrent systemic ethinyl-estradiol-containing therapy (i.e., contraceptives) and discontinuation of the hormonal therapy with continuation or brief interruption of the ABBVIE REGIMEN led to resolution in serum ALT elevation. Transient elevations in serum bilirubin (predominantly indirect) were observed in subjects receiving the ABBVIE REGIMEN with RBV, related to the inhibition of the bilirubin transporters, organic anion-transporting polypeptides (OATPs) 1B1/1B3, by ABT-450 and RBV-induced hemolysis. Bilirubin elevations occurred after initiation of treatment, peaked by study Week 1, and generally resolved with ongoing therapy. Bilirubin elevations were not associated with aminotransferase elevations. The frequency of indirect bilirubin elevations was lower among subjects who did not receive RBV.

Response of CHC genotype 4 was assessed in the phase II study PEARL-I in which 86 treatment-naïve patients were randomized to the 2 DAA combination of Paritaprevir/r – ombitasvir with vs. without RBV for 12 weeks. The SVR was 100% with RBV vs. 91% without RBV [61]. No serious SAEs or AEs leading to discontinuation were reported.

These results from pivotal studies are encouraging and the new interferon-free regimens might provide physicians with the armamentarium to cure the vast majority of patients

---

Confidential Information

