#### 9.4.1.5 Concomitant Medication

Concomitant medication - the following will be documented:

- Concomitant medication used from the time when the decision is made to initiate treatment with the ABBVIE REGIMEN until after the last dose

It should be verified by the treating physician that concomitant medication can be safely administered with the ABBVIE REGIMEN (including ritonavir) and RBV. Some medications may be contra-indicated, some may require dose adjustments due to potential for drug-drug interactions (DDIs). The investigator or qualified designee should review the concomitant medication(s) labels and screen concomitant medications at each visit for potential DDIs.

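### The by-class table of on-treatment co-medication omits profile C3 Drug A, although drugs in that profile were taken on treatment until they were replaced (minor)

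*SAP*

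**What the plan says.** SAP 4.2.8.2 plans several co-medication tables for the safety population. The first groups preferred terms by drug class, and its scope is stated directly: "Only co-medication received during treatment specified by ABBVIE regimen will be displayed". The qualifying profiles follow in brackets: "Treatment profiles: A1, A2, C1 Drug B, C2 Drug B, C3 Drug B, D".

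The profile definitions come next in the same section. Four matter here:

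- "C3 Drug A: Replaced during CHC treatment (C3A"
- "C3 Drug B: Substitute during CHC treatment (C3B"
- "A2: Permanently discontinued during CHC treatment (A2"
- "C1 Drug A: Permanently replaced at start of CHC treatment (C1A" (C2 Drug A is defined in the same words)

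The section also plans a table by profile, a table for medications of special interest and a table of treated conditions. All three consider every profile.

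Collecting information on concomitant medication is a secondary objective (Protocol 8.2.2, SAP 2). Protocol 9.4.1.5 has it documented from the decision to treat until after the last dose. It also asks for interaction screening at each visit, because some drugs may be contraindicated and "some may require dose adjustments due to potential for drug-drug interactions (DDIs".

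**The concern.** The stated scope and the profile list disagree. A drug replaced partway through treatment was co-administered with the regimen up to that point, so it lies within the scope. The list admits its substitute (C3 Drug B) but not the drug itself.

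What is at stake is the accuracy of one descriptive table on a named secondary objective. A reader of the by-class table would take it as the account of what patients took together with the regimen. A drug that was co-administered and then switched would be missing from its preferred-term row, while its replacement would be shown. The drugs left out are a particular kind, those withdrawn and replaced under treatment, and interaction screening at each visit is one process that could produce such switches.

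**Working it through.** No figure in the plan is in question, so the check compares the profile list with the SAP's own definitions and then asks what the omission does to the table.

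**Step 1. Classify the 11 defined profiles by whether the drug was taken during treatment.**

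| Profile | Meaning in SAP 4.2.8.2, paraphrased | Taken on treatment? | Listed? |
|---|---|---|---|
| A1 | continued | yes | yes |
| A2 | stopped for good during treatment | yes, until stopped | yes |
| A3 | stopped for good before treatment | no | no |
| B | stopped before, restarted after | no | no |
| C1 Drug A | replaced at start | no | no |
| C1 Drug B | substitute from start, stopped during | yes, until stopped | yes |
| C2 Drug A | replaced at start | no | no |
| C2 Drug B | substitute from start, continued | yes | yes |
| C3 Drug A | replaced during treatment | yes, until replaced | **no** |
| C3 Drug B | substitute during treatment | yes, from the switch | yes |
| D | introduced during treatment | yes | yes |

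**Step 2. Compare the sets.** Taken on treatment by definition: A1, A2, C1B, C2B, C3A, C3B, D (7). Listed: A1, A2, C1B, C2B, C3B, D (6). Difference: 7 − 6 = 1, namely C3A. The other four unlisted profiles (A3, B, C1A, C2A) are correctly outside the scope. The further category for drugs with no reported profile cannot be classified and is also not listed.

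**Step 3. Is there a rule that would justify the exclusion?** Stopping before the end of treatment does not disqualify a drug, because A2 and C1 Drug B are both listed. Being the first drug of a replacement pair is a sound reason in C1 and C2, where the switch falls at the start. It does not carry over to C3, where the switch comes later.

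**Step 4. Effect on the table.** The SAP says only that frequencies are displayed. Assume that patients are counted, and consider one patient whose drug A was replaced by drug B during treatment:

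| Situation | Preferred-term row for drug A | Class row for drug A |
|---|---|---|
| B in another class, no other listed drug in A's class | one patient too few | one patient too few |
| B in the same class as A | one patient too few | unchanged |
| B in another class, but another listed drug in A's class | one patient too few | unchanged |
| Drug A also taken under a listed profile | unchanged | unchanged |

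If records were counted instead of patients, each C3 Drug A record would be missing from both rows.

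**Step 5. Size.** The shortfall depends on the number of C3 Drug A records and on how often the two drugs share a class. The documents give neither, so no figure can be computed.

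**The case against.** The strongest reply is that little is lost. C3 Drug A has its own category in the by-profile table (tcomp_), and the special-interest (tatp_) and treated-condition (tatc_) tables consider all profiles. That stands: it would be wrong to infer that these exposures go unreported, or that every mid-treatment switch is recorded as one exposure instead of two. In the by-profile table a switch shows as both C3A and C3B. The reply does not remove the inconsistency, because none of these tables, as described, gives on-treatment frequencies by class.

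A reader might also infer that class totals are always too low. Under patient counting that does not follow, since a switch within a class leaves the class count as it was.

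A third tempting inference concerns safety. Protocol 7.1 says of ALT elevations in the development trials: "A disproportionate number of the cases were in women on concurrent systemic ethinyl-estradiol-containing therapy". One might conclude that the table would hide such a contraceptive. The documents do not support this. Protocol 7.1 describes the hormonal therapy being discontinued, not replaced, and a drug simply stopped during treatment falls under A2, which is listed. The profile definitions also record no reason for a replacement, so attributing the omitted switches to interactions or toxicity is conjecture.

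Finally, this is a descriptive table. The SVR12 regressions in SAP 4.2.7.2.1 and the adverse-event tables in SAP 4.2.8.3 do not use it. That also stands and limits the weight of the point.

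**Conclusion.** The inconsistency is real and minor. By the SAP's own definitions, C3 Drug A is the only profile with on-treatment intake that is left out of a table meant to show on-treatment intake, and no reason is given. Programmed as written, the table understates the preferred-term frequency of replaced drugs, except where the patient also took the drug under a listed profile. It understates class totals for some switches only. Both statements assume that patients, not records, are counted.

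The error can only run downward, and its size is unknown; it could be trivial. Collection of the data, the other co-medication tables, SVR12 and the adverse-event results are unaffected.

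**What to change.** In SAP 4.2.8.2, extend the list for the by-class table to A1, A2, C1 Drug B, C2 Drug B, C3 Drug A, C3 Drug B, D, and change the program filter for tcom_ to match. If the exclusion was intended, give the reason and reword the scope of the table.

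The cost is one term in the SAP and one in the filter, with no new data. One consequence needs a note: SAP 4.2.9.3 to 4.2.9.5 include co-medication tables in the third, fourth and fifth interim analyses. If those used the present filter, the final report should say that the definition changed, so that the counts are not compared as though they were alike.

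In the same edit it would help to say how drugs with no reported profile are handled, since some may have been taken on treatment, and whether frequencies count patients or records.
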